9. SAFETY EVALUATION

9.1. Demographic and Other Baseline Characteristics

Ethnicity, race, gender, and IL28B status will be summarized for all enrolled subjects by site in [Table 31](#) and by randomized treatment group in [Table 32](#). Ethnicity, race, gender, and IL28B status will be summarized for the mITT population in [Table 33](#) and the ATP population in [Table 34](#), as these covarates are used in the models described in Section 8. Ethnicity is categorized as Hispanic or Latino, or Not Hispanic or Latino. Race is categorized as American Indian or Alaska Native, Asian, Native Hawaiian or Other Pacific Islander, Black or African American, White, Multi-Racial or Unknown In accordance with NIH reporting policy. IL28B status will be categorized as CC/CT TT. Subjects may self-designate as belonging to more than one race (Multi-Racial) or may refuse to identify a race (Unknown), the latter reflected in the Case Report Form (CRF) as “No” to each racial option. Age and BMI will be summarized by site in [Table 35](#) and by randomized treatment in [Table 36](#).

Individual subject listings will be presented for all demographics ([Listing 6](#)).

9.1.1. Prior and Concurrent Medical Conditions

All current illnesses and past pre-existing medical conditions will be coded using MedDRA® dictionary version 20.1 or higher. Summaries of subjects’ current and pre-existing medical conditions will be presented by randomized treatment group and site ([Table 37](#) and [Table 38](#)).

Individual subject listings will be presented for all medical conditions ([Listing 7](#)).

9.2. Measurements of Treatment Compliance

All subjects were to receive two doses of study product in the clinic. The first dose is administered at Visit 1 (Day 0) and the second dose is administered at Visit 6 (Day 56). Dates of first treatment are presented by site in [Table 39](#) and by treatment group in [Table 40](#). The number of doses of study product administered to subjects will be presented by treatment group as part of the subject disposition table ([Table 3](#)) and will be included in the listing of subjects excluded from the primary efficacy analysis ([Listing 1](#)). A listing of compliance data is provided in [Listing 8](#).

9.3. Adverse Events

When calculating the incidence of solicited and unsolicited adverse events (i.e., on a per subject basis), each subject will only be counted once and any repetitions of adverse events within a subject will be ignored; the denominator will be the number of subjects who received study vaccination with non-missing data for the event summarized within actual treatment group. All adverse events reported will be included in the summaries and analyses. All analyses in Section 9.3 will be performed in the safety analysis population using vaccine group if a subject received one or more doses of vaccine and placebo group otherwise.

9.3.1. Solicited Events and Symptoms

Solicited reactogenicity symptoms were collected before vaccination, and then daily for 8 days post vaccination and graded on a scale of 0 (none), 1 (mild), 2 (moderate) and 3 (severe). Signs and symptoms will be categorized as either local (pain, tenderness, erythema, induration, and warmth) or systemic (fever, malaise/fatigue, myalgia/body aches, headache, nausea, vomiting, chills, arthralgia/joint pain, and abdominal pain).

Analyses will be conducted separately for each dose and over all doses. Both doses will be compared to see if a reaction to the first dose is predictive of a reaction to the second dose.

The number and proportion of subjects reporting at least one local and/or systemic solicited reactogenicity sign or symptom will be summarized for each solicited event and any solicited event by dose number along with the 95% Blaker CI (Table 41, Table 42, Table 43). The primary safety endpoint is the occurrence of severe local and/or systemic solicited events in the 8 days (Day 0-7) after each dose. The number and proportion of subjects reporting at least one severe local and/or systemic solicited reactogenicity sign or symptom will be summarized for each severe solicited event and any severe solicited event by dose number along with the 95% Blaker CI. The difference in the proportions of subjects experiencing a severe solicited event between AdCh3NSmut1/MVA-NSmut vaccine treatment group and the placebo treatment group and the 95% Exact CI of the difference will also be reported. Solicited events will be analyzed by taking the most severe response over the follow-up period and dichotomizing into a binary variable (severe versus none, mild, or moderate). A Fisher's exact test will be performed to test for the difference in the proportion of subjects reporting a severe solicited reactogenicity event. The null hypothesis is that there is no difference in proportions of subjects reporting severe solicited reactogenicity events between treatment groups, with a two-sided alternative which considers the possibility of a difference in either direction. Section 6.1 provides pseudo SAS code to use for the analyses. (Table 44, Table 45, Table 46).

For each systemic and local reactogenicity event, any systemic event, any local event, and any solicited event, the maximum severity in the 8 days (Day 0-7) after each vaccination will be summarized for the Safety population. The number and percentage of subjects reporting each event will be summarized by the maximum severity, HCV infection status, and treatment group, separately for each dose and over all doses. HCV infection status will be categorized as HCV infected if at any time throughout the study they develop HCV and categorized as HCV uninfected otherwise. For each event, the denominator is the number of subjects with non-missing data for the specific solicited reactogenicity event (Table 47, Table 48, Table 49, Table 50, Table 51, Table 52, Figure 19, Figure 20, Figure 21, Figure 22).

The number of subjects reporting a solicited adverse event will be summarized for each day post vaccination (Day 0-7) for each dose both in a summary table (Table 53, Table 54, Table 55, Table 56) and graphically in a bar chart (Figure 23, Figure 24, Figure 25, Figure 26). A comparison of the event rate for each treatment group between dose 1 and dose 2 will be presented (Table 57)

Solicited local and systemic adverse events by subject will be presented in Listing 9 and Listing 10.

9.3.2. Unsolicited Adverse Events

Adverse events will be collected through day 90. At visits following Day 90, only SAE's will be collected. Adverse events will be graded on a scale of 0 (none), 1 (mild), 2 (moderate), 3 (severe), 4 (life threatening), and 5 (death).

Adverse events will be coded to a Medical Dictionary for Regulatory Activities Terminology (MedDRA) version 20.1 or later. Verbatim description, the MedDRA System Organ Class, and Preferred Term for all adverse events will be contained in the subject data listings.

The proportion of subjects reporting at least one unsolicited adverse event will be summarized by dose and over all doses, MedDRA® system organ class (SOC) and preferred term (PT) for all subjects and each actual treatment group. Denominators for percentages are the number of subjects who received the dose being summarized. A 95% Blaker CI will be presented for each SOC and PT. (Table 58, Table 59, Table 60)

Adverse events by subject will be presented in Listing 11.

The following summaries for unsolicited adverse events will be presented by SOC, PT, dose and treatment group:

- Number and percentage of subjects by dose, HCV Infection Status, maximum severity and maximum relationship to study product including Frequency (Event level) of events for all subjects and by actual treatment received ([Table 61](#), [Table 62](#), [Table 63](#), [Table 64](#), [Table 65](#), [Table 66](#));
- Number and percentage of subjects by dose, HCV Infection Status, maximum severity and maximum relationship to study product including Frequency (Event level) of events for all subjects and by actual treatment received ([Table 67](#), [Table 68](#), [Table 69](#));
- Subject incidence and total frequency of adverse events over time (Days 1-8, Days 8-55, Days 56-63, Days 64-90) ([Table 70](#), [Table 71](#), [Table 72](#));
- Subject listing of non-serious adverse events of moderate or greater severity ([Table 73](#));
- Bar chart of total frequency of adverse events by severity and SOC ([Figure 27](#));
- Bar chart of subject incidence of adverse events by severity and SOC ([Figure 28](#));
- Bar chart of total frequency of adverse events by relationship to study product and SOC ([Figure 29](#));
- Bar chart of subject incidence of adverse events by relationship to study product and SOC ([Figure 30](#));
- For all adverse events (solicited, unsolicited, or laboratory events) occurring in 5% of subjects in any treatment group, the frequency of each event will be presented by MedDRA® system organ class, preferred term, and treatment group in [Table 74](#).
- For all adverse events (solicited, unsolicited, or laboratory events) occurring in 5% of subjects in any treatment group, the number and percentage of subjects reporting each event presented by SOC, PT, and treatment group in [Table 75](#).

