- Study personnel will review and record all AE/SAEs and concomitant medications on the appropriate data collection form.
- Approximately 23 mL of venous blood will be collected for hematology and biochemistry parameters, as described in Section 7.6.1, and performed by the local laboratory.
- Approximately 10 mL of venous blood will be collected for HCV viremia.
- Approximately 160 mL of venous blood will be collected for immunologic assays.
- Counseling on avoidance of HCV and HIV infection, and pregnancy will be conducted.
- Referral to drug treatment and needle exchange programs will be provided.

8.2.5 Day 56, Visit 6, Dose 2

(Window: Day 49 to 63)

- Eligibility criteria for receipt of Dose 2 will be reviewed with the subject see Section 5.1 and 5.2.
- Current health status will be reviewed and any changes since the last visit will be recorded.
- The vaccination site will be examined.

- Vital signs will be obtained, including oral temperature, pulse, and blood pressure.
- All concomitant medications will be reviewed for accuracy and completeness. Any new medications will be recorded and assessed for continuing eligibility.
- A targeted physical examination may be performed, as indicated, based on subject's recent clinical history since the screening visit.
- A urine or serum pregnancy test must be performed within 24 hours prior to vaccination for all female subjects of childbearing potential. Results must be negative and known prior to vaccination. If the screening visit is Day -1, a negative pregnancy test obtained at Day -1 may be used for eligibility at Day 0. If the pregnancy test is > 24 hours prior to vaccination, it must be repeated to determine eligibility.
- Approximately 23 mL of venous blood will be collected prior to vaccination for hematology, coagulation and chemistry/metabolic biochemistry parameters, as described in Section 7.6.1, and performed by the local laboratory.
- Approximately 10 mL of venous blood will be collected prior to vaccination for HCV viremia.
- Approximately 100 mL of venous blood will be collected prior to vaccination for baseline immunology assessments.

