9.3 Safety Reporting Requirements

9.3.1 Reporting Interval

All SAEs and new onset chronic illnesses will be documented from randomization through subject's last visit (Visit 26 or H09)/subject completion of all study assessments.

- New-onset chronic illnesses will be collected from randomization through a subject's last visit (Visit 26 or Visit H09). New-onset chronic illnesses are defined as any new ICD-10 diagnosis that is applied to the subject during the duration of the study, after receipt of the study agent, that is expected to continue for at least 6 months and requires continued health care intervention. To reference the International Statistical Classification of Diseases and Related Health Problems, 10th revision (ICD-10): http://www.cdc.gov/nchs/about/otheract/icd9/abticd10.htm
- Non-serious Adverse Events will be collected from randomization through 34 days post-vaccination 2 (approximately Day 90). All SAEs and AEs will be followed until they are resolved or determined by the PI to be medically stable,

even if this extends beyond the study-reporting period. Resolution of an adverse event is defined as the return to pre-treatment status or stabilization of the condition with the expectation that it will remain chronic.

At any time after completion of the study, if the investigator becomes aware of a serious adverse event that is suspected to be related to study product, the investigator will report the event to the DMID Pharmacovigilance contractor, DMID CROMS Pharmacovigilance Group.

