Table 68: Number and Percentage of Subjects Experiencing Unsolicited Adverse Events by MedDRA System Organ Class and Preferred Term, Maximum Severity, Relationship, Treatment Group, and Site-Safety Population, University of California, San Francisco

Table 69: Number and Percentage of Subjects Experiencing Unsolicited Adverse Events by MedDRA System Organ Class and Preferred Term, Maximum Severity, Relationship, Treatment Group, and Site-Safety Population, University of New Mexico

Table 70: Number and Percentage of Subjects Experiencing Unsolicited Adverse Events by MedDRA System Organ Class and Preferred Term, Day Post Dosing, and Treatment Group-Safety Population

All Subjects (N=X)													
MedDRA System Organ Class	MedDRA Preferred Term	Day 0-7 Post Dose 1			Day 8-55 Post Dose 1			Day 56-63* Post Dose 2			Day 64-90 Post Dose 2		
		n	%	Freq	n	%	Freq	n	%	Freq	n	%	Freq
Any SOC	Any PT	x	x	x	x	x	x	x	x	x	x	x	x
[SOC 1]	Any PT	x	x	x	x	x	x	x	x	x	x	x	x
	[PT 1]	x	x	x	x	x	x	x	x	x	x	x	x
	[PT 2]	x	x	x	x	x	x	x	x	x	x	x	x
[SOC 2]	Any PT	x	x	x	x	x	x	x	x	x	x	x	x
	[PT 1]	x	x	x	x	x	x	x	x	x	x	x	x
	[PT 2]	x	x	x	x	x	x	x	x	x	x	x	x

Note: N = Number of subjects in the Safety Analysis Population. For each time period, a subject is only counted once per PT.
*7 Days post receipt of Dose 2, window may vary

Tables with similar format:

Table 71: Number and Percentage of Subjects Experiencing Unsolicited Adverse Events by MedDRA System Organ Class and Preferred Term, Day Post Dosing, and Treatment Group- Safety Population-Vaccine

Table 72: Number and Percentage of Subjects Experiencing Unsolicited Adverse Events by MedDRA System Organ Class and Preferred Term, Day Post Dosing, and Treatment Group- Safety Population-Placebo

Table 73: Listing of Non-Serious, Unsolicited, Severe or Greater Adverse Events

Adverse Event	Associated with Dose No.	No. of Days Post Associated Dose (Duration)	Severity	Relationship to Study Treatment	If Not Related, Alternative Etiology	Action Taken with Study Treatment	Subject Discontinued Due to AE	Outcome	MedDRA System Organ Class	MedDRA Preferred Term
Subject ID: , Cohort: HCV +/-, Treatment Group: , AE Number:										
xxxxxx	x	xx (xxx)	xxxxxx	xxxxxxx	xxxxxxx	xxxxxxx	Y/N	xxxxxxx	xxxxxxx	xxxxxxx
Comments: xxxxxxxxxxxxxxxxxxxxxxx										
Subject ID: , Cohort: HCV +/-, Treatment Group: , AE Number:										
xxxxxx	x	xx (xxx)	xxxxxx	xxxxxxx	xxxxxxx	xxxxxxx	Y/N	xxxxxxx	xxxxxxx	xxxxxxx
Comments: xxxxxxxxxxxxxxxxxxxxxxx										

Programming Notes:

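### SAP 9.3.2 and Tables 70-72: two of the four time columns for unsolicited AEs have fixed day limits that match the dose periods only when dose 2 is given on Day 56

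*SAP*

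**What the plan says.** Among the summaries of unsolicited events, SAP 9.3.2 lists "Subject incidence and total frequency of adverse events over time (Days 1-8, Days 8-55, Days 56-63, Days 64-90" (Tables 70, 71 and 72). It gives the period as "Adverse events will be collected through day 90", with only SAEs gathered at later visits.

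The Table 70 shell, whose format Tables 71 and 72 share, has four columns. The first two are headed "Day 0-7 Post Dose 1" and "Day 8-55 Post Dose 1". The third covers Days 56-63 after dose 2, and the last is "Day 64-90 Post Dose 2". Only the third has a footnote: "7 Days post receipt of Dose 2, window may vary".

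The timing of dose 2 and of AE collection comes from elsewhere:

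- Protocol 8.2.5 targets Day 56 for dose 2, with "Window: Day 49 to 63".
- Protocol 5.2 and SAP 4.3.2 allow dose 2 up to 28 days late after a temporary contraindication.
- Protocol 9.3.1 says "Non-serious Adverse Events will be collected from randomization through 34 days post-vaccination 2 (approximately Day 90".
- SAP 4.4.6 also ends full recording of concomitant medication at 34 days after dose 2.

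**The concern.** These are the tables that show when unsolicited events occurred relative to the boost. The third column moves with dose 2, but its neighbours are not stated to move with it. For any boost not given on Day 56, the four columns as written then no longer divide the AE period into separate, complete parts. An event could be shown under the wrong dose, under two columns, or under none. The last column also stops at Day 90, whereas the protocol's period depends on the actual date of dose 2. At stake is the accuracy of a timing display, including for boosts given within the routine visit window.

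**Working it through.** **Inputs.** Let d be the study day of dose 2. The values used are d = 49, 56 and 63 (Protocol 8.2.5), 70 (the upper limit of the dose interval for the ATP population, SAP 6.3.3) and 84 (deferral counted from the Day 56 target: 56 + 28 = 84). The protocol's non-serious AE period is taken as Days 0 to d + 34.

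**The plan's own figure.** 56 + 34 = 90, so Day 90 is exact for a Day-56 boost. With d = 56 the columns 0-7, 8-55, 56-63 and 64-90 cover Days 0-90 once each.

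**Reading A, literal: only the footnoted column moves.** The columns are 0-7, 8-55, d to d+7, and 64-90.

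| d | Period ends (d+34) | Days in two columns | Days in no column | Pre-boost days under post dose 2 |
|---|---|---|---|---|
| 49 | 83 | 49-55 | 57-63 | 0 |
| 56 | 90 | none | none | 0 |
| 63 | 97 | 64-70 | 56-62, 91-97 | 0 |
| 70 | 104 | 70-77 | 56-63, 91-104 | 64-69, that is 6 |
| 84 | 118 | 84-90 | 56-63, 92-118 | 64-83, that is 20 |

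For d = 49 the last column also runs 90 - 83 = 7 days beyond the protocol's period.

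**Reading B: the neighbouring limits follow dose 2, but the last column still ends at Day 90.** The columns are 0-7, 8 to d-1, d to d+7, and d+8 to 90. No day is in two columns and no pre-boost day is under post dose 2. Protocol AE days with no column are:

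- d = 49 or 56: none.
- d = 63: Days 91-97, 97 - 90 = 7 days.
- d = 70: Days 91-104, 104 - 90 = 14 days.
- d = 84: Days 92-118, 118 - 91 = 27 days, because the third column (84-91) already holds Day 91.

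**Reading C: as B, but Day 90 means the Day 90 visit.** That is Visit 9, with a window of Day 83 to 97 (Protocol 8.2.8). If it is held on Day 97, a Day-63 boost loses nothing, since 63 + 34 = 97. A Day-70 boost still lacks 104 - 97 = 7 days and a Day-84 boost 118 - 97 = 21 days.

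**Text against shell.** The SAP text has bins 1-8 and 8-55, so Day 8 is in both. The shell has 0-7 and 8-55, with no overlap.

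**The case against.** The strongest reply is that Reading A goes against the shell's own labels. Each column is headed by dose, the footnote shows that the author meant the key post-boost column to follow dose 2, and Listing 11 records the associated dose and the days since it. A programmer using those fields would not file a pre-boost event after dose 2. This stands in part. The double counting, the gap around Days 56-63 and the 6 or 20 pre-boost days arise only under the literal reading. It does not dispose of the point, because the footnote is attached to one column and the other limits are printed as fixed days.

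Second, the protocol calls Day 90 approximate and uses a flat Day 90 itself in 8.5.1 and in Appendix D, note F. The schedule also switches to SAEs only after Visit 9. Reading C is therefore open, and under it the loss after a Day-63 boost can be zero.

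Third, the 14 and 27 days need a boost outside the routine window, and more than 70 days is an ATP exclusion. That is correct. Tables 70-72 use the safety population, however, so those subjects stay in them.

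A reader might also infer that the SAP text leaves the dosing day out of every bin. The documents do not support that. The SAP elsewhere numbers that day as Day 1 (Table 117; the notes to Listings 7 and 21), and on that count Days 1-8 are the shell's Days 0-7. Day 8 is double-counted on either numbering.

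**Conclusion.** The point holds and is minor. Two of the four columns are tied to fixed days that agree with the dose periods only for a Day-56 boost, and the literal Day 90 end replaces a period that the protocol defines from dose 2. On the reading most consistent with the shell's labels (B), the gap is 7 days for the latest in-window boost, or none if Day 90 means a Visit 9 on Day 97. For boosts deferred to Day 70 or Day 84 it is 14 or 27 days. The larger misplacement needs the literal reading. The Day 84 limit assumes that the 28-day deferral runs from the Day 56 target. The number of subjects boosted off Day 56 is not known, and both arms are treated alike.

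A reader might infer that reported events drop out of the safety analysis, contrary to SAP 9.3, which says that all reported AEs are included. The documents do not show this. That sentence does not require every event to appear in every table. The SAE analyses, the solicited-event analyses, by-dose Tables 58-66 and Listing 11 do not use these columns. Nor do the tables bear on whether AE follow-up lasts long enough, which depends on the visit windows.

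**What to change.** In the SAP 9.3.2 text and in Tables 70-72, use four columns defined from the actual dose dates:

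1. Days 0-7 after dose 1.
2. Day 8 to the day before actual dose 2 (to Day 90 if dose 2 was not given).
3. Dose 2 to dose 2 + 7 days.
4. Dose 2 + 8 to dose 2 + 34 days.

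For dose 2 on Day d these hold 8 + (d - 8) + 8 + 27 = d + 35 days, which is exactly Days 0 to d + 34. For d = 56 they return the present shell. State the non-serious AE period in 9.3.2 as running through actual dose 2 + 34 days. Protocol 9.3.1 gives no end for a subject without dose 2, so the Day 90 limit there is a choice that keeps the SAP's present figure.

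The cost is one sentence and new column headers. No new data are needed, since Listing 11 already carries the dose number and the days since that dose.

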9.4. Deaths, Serious Adverse Events and other Significant Adverse Events

The primary safety endpoint is the occurrence of vaccine-related serious adverse events (SAEs) from the time of first vaccination through the entire study period. The number of subjects, the percentage of subjects who experienced vaccine-related SAEs, and the 95% Blaker confidence interval for the proportion of subjects who experienced vaccine-related SAEs will be presented by treatment group and study visit for each dose and across all doses. In addition, the difference in proportions between the AdCh3NSmut1/MVA-NSmut vaccine group and the placebo group and 95% Exact confidence intervals will be presented. The proportion of subjects in each treatment group who experience vaccine-related SAEs through the entire study period will be tested using a Fisher's exact test at the 5% two-sided level of significance level without adjustment for multiplicity in the safety analysis population ([Table 76](#)). See Section 6.1 for pseudocode for calculating p-values and CIs. SAEs will be summarized by treatment group, PT, SOC, maximum severity and relationship for each dose and over all doses ([Table 77](#), [Table 78](#), [Table 79](#), [Table 80](#), [Table 81](#), [Table 82](#)).

A listing of all serious adverse events will be presented, including Subject ID, treatment group, Adverse Event Description, Study Day the Event became Serious, Reason Reported as an SAE, Relationship to Treatment, Alternate Etiology if not Related, Outcome, and Duration of Event in days ([Table 83](#)). A listing of deaths will be presented in [Table 84](#).

